### **Imaging data analyses**

We will employ a multilevel approach to data analysis (1) image analysis (post-processing), (2) statistical hypothesis testing and modeling using summary imaging measures and clinical variables (these two analyses will use a summary parameterization of the fMRI and DTI data, which are the presence or absence of activation within the prescribed regions of interest (ROIs) defined for each modality (e.g., amygdala or medial prefrontal cortex for fMRI data) or integrity of white matter tracts connecting amygdala and medial frontal regions (e.g., number of white matter fibers or FA values) which will be based on the composite MRI data, and (3) image analysis that allows for modeling changes over time while considering the effect of covariates in hierarchical linear modelling (HLM). Our analyses will be corrected for multiple comparisons at a  $p < 0.05$  level to limit the possibility of false positives while maintaining sufficient power to detect effects of interest.

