## **STUDY DESIGN OVERVIEW**

Our plan is to investigate the cerebral underpinnings of emotion and stress processing in 88 individuals with confirmed PNES and 88 individuals with confirmed PTE and 88 individuals with a history of TBI without seizures (PNES or PTE) matched for psychiatric comorbidities (TBI control subjects – CS). In addition to the between group comparisons (PNES vs. PTE vs. CS), we will examine the changes in brains' response to fMRI probes after receiving treatment (CBT-Sz), a non-pharmacologic therapeutic approach that is used for the treatment of difficult to control seizures in patients with PNES and PTE. All participants in the 3 groups will receive fMRI scans at approximately 13 week intervals. Including CS in the neuroimaging and symptom surveys portion will allow us to determine the stability of signals between and within the individuals and to control for the effects of psychological and psychiatric comorbidities.

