## **SPECIFIC AIMS**

**Specific Aim 1:** To compare neural correlates of response to fMRI stimuli before and after cognitive challenge (CBT-Sz). Individuals with PNES and PTE will be compared to individuals with a history of TBI who do not have PTE/PNES in order to control for common comorbidities including depression, anxiety and PTSD, and to show fMRI signal stability between and within the individuals.

**Hypothesis 1:** We hypothesize, based on our preliminary data, that baseline fMRI in all groups will show aberrant responses to stress and abnormal emotional processing between those with seizures vs. those without seizure disorders, with differences predominantly observed in the medial frontal cortices and amygdala with these differences being most abnormal in the PNES group.

**Specific Aim 2:** To investigate changes in neural circuitry for emotional processing in individuals with seizures after receiving CBT-Sz and to correlate these changes with symptomatic improvement.

**Hypothesis 2:** We hypothesize that CBT-Sz will lead to changes in the fMRI signals and in amygdala connectivity as shown with DTI and fMRI. This change will, in turn, be predicted by the magnitude of clinical responses defined by seizure frequency improvement over time and secondarily by targeted behavioral measures.

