**4.1 Power analysis**

Our power analysis is based on our preliminary neuroimaging and clinical data, and data regarding number needed to be evaluated in neuroimaging studies to reliably demonstrate differences between

groups in cognitive studies. Based on our preliminary data for the fMRI stress task ([name], unpublished), given the large effect size (Cohen's *d*) of 0.88, when the sample size is 14 people per group, a *t*-test of two related samples with 5% two-sided significance will have about 85% power to reject the null hypothesis that there is no difference in pre-intervention and post-intervention fMRI measures in limbic structures (medial frontal cortices and amygdala). In a recently analyzed study of the emotional faces fMRI task, 12 participants per group were sufficient to show significant differences between participants with PNES, ES and controls in emotion control brain circuits. ([name], et al, HMB, under review) It is possible that the effect size may not be as large in ES as it is expected in PNES. For this study, we expect 25 participants per group to be sufficient to account for the possibility of a more conservative effect size (e.g., 0.65). With the expected 50% responder rate to the cognitive challenge (CBT-Sz), 50 per each group (PNES, PTE, controls) will allow to test the within groups and between groups differences. Adding additional 24 participants per group will allow controlling for two most frequent comorbidities in our patients (12/condition; depression / anxiety and PTSD; 50+24=74). With anticipated attrition rate of up to 20% ( $74 \times 0.2 = 14$  to 15 per group) a sample of 88 Veterans with PNES, 88 Veterans with PTE, and 88 Veterans with TBI but no PNES/PTE can address the study hypotheses and control for the confounders including comorbidities.

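### The fMRI summary for hypothesis testing is presence or absence of activation per region, while the power calculation implies a continuous measure; the flag discards information, most directly in the between-group tests

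*Combined protocol and SAP*

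**What the plan says.** The Imaging data analyses text under section 4.1 sets out three levels.

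- Level (1) is image post-processing.
- Level (2) is "statistical hypothesis testing and modeling using summary imaging measures and clinical variables".
- Level (3) is "image analysis that allows for modeling changes over time while considering the effect of covariates in hierarchical linear modelling (HLM"). Its outcome scale is not stated.

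Levels (1) and (2) share one summary of the imaging data. For fMRI it is "the presence or absence of activation within the prescribed regions of interest (ROIs) defined for each modality", with amygdala and medial prefrontal cortex given as example regions. For DTI it is tract integrity, with fibre counts or FA values as examples, so DTI stays quantitative. The sentence adds that the summary rests on composite MRI data, a term it does not define.

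Section 4.1 gives one power percentage. With Cohen's d of 0.88 and 14 people per group, a t-test of "two related samples with 5% two-sided significance will have about 85% power to reject the null hypothesis" of no pre/post difference in limbic fMRI measures. The next step, "we expect 25 participants per group to be sufficient to account for the possibility of a more conservative effect size (e.g., 0.65"), carries no power figure. The later steps (50, then 74, then 88 per group) carry none either.

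The Study Design Overview plans comparisons of PNES, PTE and controls. Hypothesis 1 expects group differences "with differences predominantly observed in the medial frontal cortices and amygdala", which closely match the example regions for the fMRI summary.

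**The concern.** A paired t-test and Cohen's d describe a measure with a mean and a standard deviation. A present/absent call has neither in that sense. The measure that supports the sample size and the measure named for hypothesis testing are therefore on different scales, and nothing in the text connects them.

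The natural reading is a flag for each participant, because level (2) models the summary together with clinical variables and so needs one value per person. On that reading, two groups can differ clearly in mean amygdala response and still look alike, if most people in both fall on the same side of the threshold. Hypothesis 1 is most directly exposed: it is a between-group claim about the regions that the flag would describe. What is at stake is power and resolution in level (2) fMRI tests, given up without any saving in scanning or processing.

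**Working it through.** **1. The plan's own figure.** Inputs from section 4.1: d = 0.88, n = 14, paired t-test, two-sided 5%.

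- Noncentrality = d√n = 0.88 × √14 = 3.293; df = 13; critical t = 2.160.
- Power from the noncentral t = 86.0%, which agrees with the stated value of about 85%.

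A two-sample t-test with 14 per group gives 61.1%, so the stated figure belongs to a paired comparison of a continuous measure. That the measure is continuous is inferred from the test and effect size; section 4.1 says only fMRI measures.

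**2. Inputs for the between-group illustration.**

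- From the plan: 88 per group and attrition up to 20%, so 88 × 0.8 = 70.4, taken as 70 evaluable per group.
- From the plan but borrowed: d = 0.65. Section 4.1 introduces it after a pre/post calculation; here it stands for a difference between groups.
- Assumed, not in the documents: a normally distributed regional signal behind the flag, and reference-group activation of 25%, 50%, 75% or 90%.
- Two-sided 5%, no multiplicity correction. The plan does intend a correction, which would lower both columns of power.

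**3. Continuous measure.** Two-sample t-test: noncentrality = d√(n/2) = 0.65 × √35 = 3.845; df = 138; critical t = 1.977. Power = 96.8%.

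**4. Present/absent flag.** If a proportion p0 of the reference group activates, the other group activates at p1 = Φ(Φ⁻¹(p0) ± 0.65). For example, with p0 = 0.25, Φ⁻¹(0.25) = −0.674, so p1 = Φ(−1.324) = 0.093 or Φ(−0.024) = 0.490. Power of the pooled two-proportion z-test is by exact enumeration at 70 per group.

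| Reference activation | Other group lower: p1 | Power | Other group higher: p1 | Power |
|---|---|---|---|---|
| 25% | 0.093 | 71.3% | 0.490 | 84.4% |
| 50% | 0.258 | 84.6% | 0.742 | 84.6% |
| 75% | 0.510 | 84.4% | 0.907 | 71.3% |
| 90% | 0.736 | 72.8% | 0.973 | 44.2% |

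Against 96.8% for the t-test, the flag gives 71–85% over 25–75% activation, a loss of 12 to 26 percentage points (96.8 − 84.6 = 12.2; 96.8 − 71.3 = 25.5). The 44% is a ceiling case: 90% already activate and the other group activates more.

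**5. Which tests are reached.** The between-group fMRI comparisons fit level (2) most directly. Pre/post change, and the Aim 2 correlation of change with symptomatic improvement, could fall under level (2) because of its clinical variables, or under level (3) because of its modelling of change. The text does not settle this, so no size is attached to them here. DTI measures are not affected.

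**The case against.** The strongest counter-reading is that the phrase does not describe a 0/1 outcome at all. The summary also serves level (1) post-processing and is said to rest on composite data, so it could mean activation above threshold on a processed or group map. The power figures above would then not apply, and an undefined term would remain. The text does not exclude this. It is the weaker reading, though, because a summary modelled with clinical variables needs a value per participant.

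Loose wording is also plausible: section 4.1 suggests that the authors had a continuous measure in mind. If so, the correction is one sentence. The appendix cited under MRI tasks scanning protocol was not available and might define the measure.

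The size of the loss depends on assumptions. With d = 0.88 borrowed in the same way, the flag has 90–98% power at 25–75% activation (95% or 61% at 90%), against 99.9% for the t-test. That the flag does worse is built into the model, since thresholding a normal variable always loses information. These points limit the size of the loss. They do not remove the mismatch between the two sections.

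A reader might infer two stronger things. One is that the 85% is wrong because the test behind it uses the flag. The documents do not say so: change over time is assigned to level (3), and the 85% is correct on its own basis. The other is that 88 per group is inadequate. Nothing here shows that; the flag keeps 71–85% power over most of the illustrated range. Nor is "With the expected 50% responder rate to the cognitive challenge (CBT-Sz") an activation rate that could fill the gap. It concerns response to treatment.

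**Conclusion.** The point holds as a mismatch with an easy improvement. The plan names a present/absent fMRI summary for hypothesis testing, keeps DTI quantitative, and gives a power percentage only for a calculation that implies a continuous measure. Confidence in that textual mismatch is high. Confidence in the consequence is moderate: it rests on reading the summary as a flag per participant, on the latent normal signal and activation rates assumed above, and on the borrowed d. On that basis the loss falls most directly on the fMRI comparisons of Hypothesis 1. Whether tests of change and the Aim 2 correlation share it depends on the level at which they are run. It should be fixed, because the better measure costs almost nothing.

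**What to change.** Under Imaging data analyses, make the mean contrast estimate (beta or percent signal change) in each pre-specified region, per participant, task contrast and scan, the fMRI summary for level (2) tests and for any test of change, at whichever level it is run. This matches the continuous measure implied by section 4.1. Keep presence or absence of activation as a descriptive report only. If the MRI appendix already defines such a measure, cite it there.

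The cost is analysis wording. The estimates come from the same first-level models that produce the activation maps, so no extra scanning, data collection or participants are needed.

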### **4.2 Quality Control and Data Management:**

The accuracy and reliability of MRI data from each site are paramount to the success of this study. Quality control and quality assurance (QA) are essential in this process. A periodic QA review process will occur quarterly with the study QA staff and the research staff.

### **4.3 Withdrawal of Participants**

Protocols are established to address and contain any high risk aspects of the proposed works, including increase in seizures or depressive symptoms. If during the study participants are found to develop medical or mental health problems, they will be referred for appropriate treatment, as indicated in the safety protocol. If clinically indicated, he/she will be withdrawn from the study. If a participant develops nonepileptic psychogenic status (NEPS) or status epilepticus, the participant will be referred to the local emergency department for observation, and if clinically indicated, will be withdrawn from the study.

Participants who decide that they do not want to start or finish the CBT-Sz sessions will be asked to continue completing self-reports and assessments and the second fMRI, in order to compare completers with any non-completers.

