**Follow-up assessment:**

The PNES/ES follow-up questionnaire (ESTXFU) is used after the treatment portion of the study and will be used for secondary longitudinal analysis. There will be 2 follow up sessions (months 8 & 12 after the participant's first CBT-Sz session) the interviewer will ask participants questions regarding the seizure frequency and treatments using this questionnaire (ESTXFU). These sessions will be conducted by research staff either in person or via phone call.

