#### **Safety Monitoring Plan**

The Principal Investigator will have primary responsibility for day-to-day monitoring of participant safety, and the quality of operations in all data collection, data cleaning and transfer activities.

All adverse events (AEs) occurring during the course of the study will be collected, documented, and reported to the PI. The study investigators will follow all AEs to the point of a satisfactory resolution. A study participant may be withdrawn from the study if the medically responsible investigator determines it is the best decision in order to protect the safety of a participant. All AEs will be assessed to determine if they meet criteria for a Serious Adverse Event (SAE). SAEs will be reported to each IRB according to their policy. In the event that a participant either withdraws from the study or the investigator decides to discontinue their participation due to a SAE, the participant will have appropriate follow-up medical monitoring. Monitoring will continue until the problem has resolved or stabilized with no further change expected, or it is deemed to be clearly unrelated to participation in the study.

If during the study participants are found to develop suicidal intent, medical or other mental health problems they will be triaged for appropriate care, according to good clinical practice and the safety protocol.

This multi-site study includes a Data Monitoring Committee (DMC). See Addendum F for the DMC plan.

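### Section 4.3 keeps collecting outcomes from participants who choose to stop CBT-Sz but not from those the investigator withdraws, so later data can be lost in a probably small group more likely to have worsened

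*Combined protocol and SAP*

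**What the plan says.** Section 4.3 opens with the risks it is meant to manage: "Protocols are established to address and contain any high risk aspects of the proposed works, including increase in seizures or depressive symptoms". It then gives two rules.

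- **Clinical withdrawal.** A participant who develops medical or mental health problems is referred for treatment, and "If clinically indicated, he/she will be withdrawn from the study". Nonepileptic psychogenic status or status epilepticus leads to emergency referral and, again if indicated, to withdrawal from the study.
- **Voluntary non-completion.** Participants who decide for themselves not to start or finish CBT-Sz "will be asked to continue completing self-reports and assessments and the second fMRI, in order to compare completers with any non-completers".

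The Safety Monitoring Plan gives the investigator a general power: "A study participant may be withdrawn from the study if the medically responsible investigator determines it is the best decision". For a participant who withdraws, or whom the investigator discontinues because of a serious adverse event, it adds that "the participant will have appropriate follow-up medical monitoring", lasting until the problem resolves, stabilises or is clearly unrelated to the study.

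Two other places matter. Hypothesis 2 (Specific Aims) says the imaging change will be "predicted by the magnitude of clinical responses defined by seizure frequency improvement over time". Section 3.7 (Follow-up assessment) says the month 8 and 12 questionnaire "will be used for secondary longitudinal analysis", and of those contacts: "These sessions will be conducted by research staff either in person or via phone call".

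**The concern.** The protocol has already accepted that stopping therapy need not mean leaving data collection, and it says why: to compare completers with non-completers. It applies this only to people who choose to stop. Staff who read the rule for clinical withdrawal beside the rule for voluntary stopping would reasonably end collection for the first group.

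That loss is unlikely to be random. The risks named in Section 4.3, together with status events, overlap with seizure frequency, which is the response measure in Hypothesis 2, and with the BDI-II, which is given at every session. There is no untreated seizure arm, and the TBI controls have no seizures. Clinical improvement is therefore a before-and-after estimate, and selective loss of worsened participants passes straight into it. The hierarchical linear model named under Imaging data analyses can use partial data, but a standard fit relies on a missing-at-random assumption that withdrawal for worsening may violate. No method for missing data is stated.

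At stake are later seizure logs, self-reports, the month 8 and 12 interviews, and the second scan if it has not yet been done. The comparison of completers with non-completers would also leave these people out.

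**Working it through.** **The text, side by side**

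| | Chooses to stop CBT-Sz | Withdrawn by the investigator |
|---|---|---|
| Self-reports and assessments | asked to continue | not mentioned |
| Second fMRI | asked to continue | not mentioned |
| Follow-up stated | study assessments | medical monitoring until the problem settles |

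The medical monitoring is safety follow-up. It does not provide for seizure logs, scales or the month 8 and 12 interviews.

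**The plan's only loss figure.** Section 4.1 allows up to 20% attrition from all causes: 74 × 0.2 = 14.8, and 74 + 14.8 = 88.8, which agrees with the stated 88 per group. It does not separate clinical withdrawals from other losses.

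**Assumptions (not from the documents).** The share withdrawn, w, is 2% or 5%. Clinical change X is standard normal, with higher values better. The true correlation r between clinical and imaging change is 0.30.

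Counts: 0.02 × 88 = 1.8 and 0.05 × 88 = 4.4 per group; 0.02 × 176 = 3.5 and 0.05 × 176 = 8.8 of the 176 receiving CBT-Sz.

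**Case (a): all withdrawn are the very worst.** With z the w-quantile of the normal and φ its density:

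- overstatement of the mean: L = φ(z)/(1 − w)
- SD among those retained: s = √(1 + zL − L²)
- correlation among those retained: r′ = r·s/√(1 − r² + r²s²)

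For w = 0.02: L = 0.049, s = 0.947, r′ = 0.285. For w = 0.05: L = 0.109, s = 0.900, r′ = 0.272.

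**Case (b): half of the worst 2w are withdrawn.** The mean shift is 0.5·φ(z)/(1 − w), with z now the 2w-quantile. For w = 0.02: shift 0.044, s = 0.960, r′ = 0.289. For w = 0.05: shift 0.092, s = 0.934, r′ = 0.282.

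**Case (c): half of the withdrawals are unrelated to clinical change and half are the worst.** Use the formulas of (a) with w/2 in place of w, because the random half adds no bias.

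**Case (d): all withdrawals are unrelated.** No bias.

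| Case | Mean overstated (SD), 2% / 5% | Correlation (true 0.30), 2% / 5% |
|---|---|---|
| (a) | 0.049 / 0.109 | 0.285 / 0.272 |
| (b) | 0.044 / 0.092 | 0.289 / 0.282 |
| (c) | 0.027 / 0.060 | 0.291 / 0.283 |
| (d) | 0 / 0 | 0.30 / 0.30 |

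**Scale.** With 88 per group, the standard error of a mean is 1/√88 = 0.107 SD, and that of a correlation of 0.30 is (1 − 0.09)/√87 = 0.098. The largest bias in the mean is about one standard error. The largest in the correlation, 0.300 − 0.272 = 0.028, is well below one.

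**Responder rate.** Section 4.1 expects 50%, or 44 of 88. If 4 non-responders are lost, the observed rate is 44/84 = 52.4%. If 8 are lost, it is 44/80 = 55.0%.

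**The case against.** The best reply is that this reads silence in an incomplete file as a gap. Section 4.3 points to a safety protocol that sits in an appendix, and the data monitoring plan is in Addendum F; neither was available. Nothing says that outcome collection must stop. That stands as a limit: the appendix may settle the matter.

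The link to worsening is also looser than it first appears. An increase in seizures or depressive symptoms is named as a risk to contain, not as a criterion for withdrawal. Referral comes first, and withdrawal is not automatic. The section on potential risks describes symptom increase from treatment as unlikely, and some withdrawals will be for unrelated medical problems. This stands too, and is why cases (b) to (d) are shown beside (a). An association with worsening remains a fair inference, but its strength is assumed.

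The figures also treat withdrawn participants as contributing nothing, whereas logs and BDI-II scores from before withdrawal exist and would reduce the bias. And the remedy barely reaches the imaging analysis of Hypothesis 2, which needs a second scan that may not be advisable. Both points are correct. The effect on that correlation is small and attenuating, so it works against the hypothesis rather than for it.

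These points limit the size of the problem. They do not remove the difference between two adjacent rules in the same section.

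**Conclusion.** The concern holds. As written, Section 4.3 and the Safety Monitoring Plan provide continued outcome collection for voluntary non-completers and only medical follow-up for participants the investigator withdraws. The consequence is a possible loss of later clinical data in people more likely to have worsened, so average improvement among those analysed can be slightly overstated.

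The size is probably small: 0.03 to 0.11 SD where withdrawal is at least partly related to worsening, and zero if it is unrelated. This rests on assumed withdrawal rates of 2% and 5%, normally distributed change, and no use of data from before withdrawal. The case for acting rests on low cost and on the fact that outcomes not collected at the time cannot be fully recovered, not on a large expected bias. Confidence is medium, because the appended safety protocol could not be read.

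**What to change.** In Section 4.3 and the Safety Monitoring Plan, separate stopping CBT-Sz or MRI from leaving data collection, and leave the withdrawal criteria as they are.

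- Unless consent is withdrawn, ask participants discontinued by the investigator to continue seizure logs, self-reports and the month 8 and 12 contacts, by phone where that is easier.
- Do the second fMRI only if the investigator judges it safe, since the session includes a stress task with negative feedback.
- Record the reason for discontinuation and keep these participants in the analysis as non-completers.
- Add one sensitivity analysis of seizure-frequency change that assumes an unfavourable outcome for those without later data.
- Report how many lack a second scan because of clinical withdrawal.

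If the appended safety protocol already provides this follow-up, a cross-reference in Section 4.3 is enough.

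The cost is small: protocol wording, phone follow-up for an assumed 4 to 9 participants on existing forms, and one extra analysis. The wording would probably need amendment at the review boards listed in Section 5.0. Unwell participants would be asked for more questionnaires (Section 3.7 puts the self-reports at 45 to 75 minutes), and some will refuse. Some scans will still be missing, the imaging correlation cannot be fully protected, and the response estimate may come out slightly less favourable.
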